2.5 Dose Rationale

Topical Dosing:

In addition to the safety pharmacology and toxicology studies that were completed to support development of INCB018424 PHOSPHATE CREAM. The relative bioavailability of INCB018424 PHOSPHATE CREAM was markedly (~ 90%) lower than that following oral administration. In vitro metabolism studies strongly suggest that cytochrome P450 (CYP) 3A4 is the predominant CYP isozyme responsible for the metabolism of INCB018424 PHOSPHATE CREAM.

INCB018424 PHOSPHATE CREAM has been evaluated in over 200 subjects with plaque psoriasis in 3 clinical studies with dosing of 1 to 3 months' duration. Study INCB 18424-201 was a double-blind, vehicle-controlled, rising-dose, safety, tolerability, PK, and preliminary efficacy study of INCB01824 1% cream applied QD and 1.5% cream applied BID. All adverse events (AEs) were mild to moderate in intensity and most judged unrelated to study medication, with no associated serious AEs (SAEs) or withdrawals. Laboratory and ECG evaluations did not suggest any safety issues, specifically no instances of neutropenia, thrombocytopenia, or leukopenia.

INCB 18424-202 was an open-label, multicenter, sequential-cohort, dose-escalation, safety, tolerability, PK, pharmacodynamics (PD), and preliminary efficacy study of INCB018424 PHOSPHATE CREAM 1.0% or 1.5% applied to 2% to 20% BSA QD or BID for 4 weeks. Application area increased sequentially, and alternative dosing paradigms were explored at the highest application area. The efficacy analyses collectively demonstrated efficacy of all 5 regimens of INCB018424 PHOSPHATE CREAM in psoriasis. The incidence of all reported AEs, the clinical laboratory results, vital signs, and ECG findings showed no confirmed safety signals or trends. Mean topical bioavailability ranged from 3.4% to 5.2% with no significant inhibition of cohort mean PD. Overall, INCB018424 PHOSPHATE CREAM (1.0% or 1.5%) was demonstrated to be safe and well tolerated when applied QD or BID for 28 days to plaque psoriasis affecting 2% to 20% of the BSA.

INCB 18424-203 was a double-blind, randomized, multicenter, parallel group, vehicle-controlled dose-ranging study with application of INCB018424 PHOSPHATE CREAM or vehicle in subjects with stable plaque psoriasis. Overall, INCB018424 PHOSPHATE CREAM (0.5%, 1.0%, or 1.5%) was demonstrated to be safe and well tolerated when applied QD for 12 weeks to plaque psoriasis affecting up to to 20% of the BSA.” (Investigator’s Brochure)

2.6 Risks and Benefits

Benefits:

Others with LP may benefit in the future from what we learn in this research study. It is possible their symptoms could also improve while being treated with this study drug

Risks:

The following adverse events were reported as very common Side effects associated with the use of INCB018424 PHOSPHATE CREAM:

- Occurring in greater than or equal to 10% of subjects), common (occurring in 1-10% of subjects), and rare (occurring in 0.1% of subjects) side effects occurring in 203 subjects with psoriasis treated with INCB018424 PHOSPHATE CREAM up to 1.5% twice daily strength (the highest strength to be used in this study) in 3 previous studies. Additionally, 54 subjects with alopecia areata (immune-related condition of hair loss) are participating in an ongoing study.

Very Common (affecting more than 10 in every 100 patients)
No adverse event was seen in more than 10% of the psoriasis subjects treated with INCB018424 PHOSPHATE CREAM up to 1.5% twice daily

•

Common (affecting less than 10 in every 100 patients)	
Upper respiratory tract infection/nasopharyngitis (common cold)	Abdominal pain (stomach pain)
Application site irritation (irritation on skin where study treatment is applied)	Muscle strain
Headache	Throat Pain
Change in ECG tracing	Psoriasis (skin disorder under treatment)
Pruritus (itching)	Blood sugar increased
Sinusitis (sinus infection)	Cholelithiasis (stone in gall bladder)
Back Pain	Cough
Diarrhea	Cystitis (irritation of bladder)
Dry Skin	Skin redness
Liver enzyme increased	Bulging disk in back
Gastroenteritis (vomiting/diarrhea caused by virus)	Blood cell count decreased
	Pneumonia (lung infection)
	Fever
	Skin peeling

Common (affecting less than 10 in every 100 patients)	
Influenza (flu)	Toothache

Rare but Serious
In seven out of 203 patients treated, serious adverse events were observed but were considered unrelated to INCB018424 PHOSPHATE CREAM use. Due to the number of patients studied to date, rare serious adverse events cannot be predicted with any certainty.

Photosensitivity:

There may be a risk of skin reaction to the combined exposure of INCB018424 PHOSPHATE CREAM and sunlight.

Hematologic abnormalities:

INCB018424 taken systemically can inhibit the growth of blood cells. Low blood cells can make subjects more susceptible to infections by bacteria, virus, and fungi. The risk is low with systemic therapy and was not noted with topical therapy but subjects will be monitored for any signs of inhibition of their blood counts.

Infection risk:

There is a theoretical increase in risk of infection with topical use of INCB018424 PHOSPHATE CREAM. This will be monitored for.

INCB018424 may increase risk of infections and reactivation of latent infections such as Tuberculosis or Valley Fever. Serious bacterial, fungal and viral infections were observed in patients receiving INCB018424. Please seek medical advice if signs or symptoms suggestive of infection occur.

Allergy:

It is possible that some people could have an allergic reaction to INCB018424 PHOSPHATE CREAM.

Cancer Risk:

INCB018424 PHOSPHATE CREAM may have the potential to affect subject's immune system; they may be at increased risk for infections and possibly cancer. Live vaccines should not be given concurrently with INCB018424 PHOSPHATE CREAM.

Pregnancy Risk:

The effect of the study drug on a fetus (developing baby still in the womb), or on a breastfeeding infant, is unknown and may be harmful. Because of these risks, women cannot take part in this study if they are pregnant or breastfeeding.

Skin biopsy:

A skin biopsy is generally a safe procedure, but some potential risks may include local pain, mild local bruising, bleeding, scarring, and an infection at the site where the skin biopsy was performed. If a topical antibiotic is used afterwards, then there is a small risk of an allergic reaction.

Chest X-ray:

Subjects will be exposed to radiation from the chest x-ray. The amount of radiation has a low risk of harmful effects.

Blood draw:

The risks of drawing blood include pain, bruising, lightheadedness, and/or fainting, or rarely, infection at the site of the needle stick.

Other:

As with all research, there is a chance that confidentiality could be compromised; however, we take precautions to minimize this risk.

3 Study Objectives

Primary Objective:

To determine the efficacy of INCB018424 PHOSPHATE CREAM as measured by the change in Modified CAILS score of the index treatment and control lesion (weeks 0 and 4) and changes in lesion count (week 0 and 4)

Secondary Objective:

To determine the efficacy of INCB018424 PHOSPHATE CREAM and the duration of response after discontinuation as measured by the change in Pruritus NRS, (week 0 to week 4, week 0 to week 8, weeks 4 to 8, weeks 8 to 12), Change in Skindex-16 (week 0 to week 4, weeks 4 to 8, weeks 8 to 12), Change in Physician Global Assessment (PGA) (week 0 to week 4, week 0 to week 8, weeks 4 to 8, weeks 8 to 12), Change in BSA (week 0 to week 4, week 0 to week 8, weeks 4 to 8, weeks 8 to 12), Change in Modified CAILS (week 0 to week 8, weeks 4 to 8, weeks 8 to 12).

Exploratory Objectives:

To predict responses and examine the pharmacodynamics of treatment through the identification of unique biomarkers and transcriptomic changes of LP at week 0 and utilizing RNA sequencing on responsive and non-responsive tissue at week 4 To correlate these biomarkers with measures of global response: Modified CAILS, PGA, BSA, and lesion count.

4 Study Design

4.1 General Description

This is a single center, exploratory, open-label, single-arm design study of 12 patients. Treatment naïve and treatment refractory patients with LP will be treated with INCB018424 PHOSPHATE CREAM. Patients who are non-responders, to physician choice standard of care, will undergo a washout period and will be enrolled in the study.

Multiple safety studies have been conducted with INCB018424 PHOSPHATE CREAM (see Safety) and a dose of 1.5% cream BID on up to 20% BSA is deemed safe. (Investigator's Brochure) The Within each cohort, the maximum reduction from baseline in the total psoriasis lesion assessment scores for the treated lesions was observed at the end of treatment (Day 28). (Investigator's Brochure) Therefore, we propose a single center, exploratory, open-label, single-arm design study of 12 patients. Treatment naïve and treatment refractory patients with LP will be treated with INCB018424 PHOSPHATE CREAM.

Individuals with LP involving less than 20% of the BSA will be eligible. Individuals must have 4 lesions at baseline, however, a minimum of 10 lesions is ideal, which are at least 5mm in diameter. 10 lesions are ideal as 2 lesions will be index lesions and 8 or more lesions will be selected from as responsive or non-responsive at 4 weeks. All lesions except for one index lesion will be treated and all lesions will be annotated, photographed, and scored. The rationale for a minimum of 8 lesions is based upon the assumption of a 50% response rate at 2 weeks. With 8 lesions, there would be a less than 1% chance that all 8 lesions would respond. Ideally, the 2 index lesions will be 10mm in diameter but this is not a requirement. Prior treatment will be allowed; however, a washout period of 2 weeks for topical and 4 weeks for systemic agents is required. At the washout period, individuals will undergo evaluation with a PGA, BSA calculation, and have the 2 largest, representative lesions selected for evaluation using a modified CAILS score lesion A- treatment index lesion and B-index control lesion. The determination of which lesion receives treatment and which is a control will be determined randomly. The additional lesions will be photographed, measured, scored, and recorded with Modified CAILS scores as well. The later calculations will be used for the determination of responsive and non-responsive lesions. Additional Pruritus measures using the NRS and Skindex-16 will be collected at that time.

Individuals will then initiate treatment on all lesions of LP BID and will be evaluated weekly and assessed by PGA, BSA, lesion count; Modified CAILS, Pruritus NRS, and Skindex-16 between weeks 0-4 (see Appendix). Week 4 will be the primary endpoint; however therapy will be continued for an additional 4 weeks. Therapy will be stopped and the individuals will be evaluated at week 8 and assessed by PGA, BSA, lesion count, Modified CAILS, Pruritus NRS, and Skindex-16. Laboratory and safety monitoring will occur at weeks 1, 2, 3, 4, and 8, and 12. 3D Photographs will be taken at weeks 0, 1, 2, 3, 4, 8, and 12. Individual lesions will be circled at that time and the exact volume of each lesion will be measured. Up close photos will be taken of the disease and normal tissues attained at weeks 0 & 4.

Tissue will be collected for RNA sequencing at week 0 and 4. Blood collection will include the isolation at week 0, 2, and week 4, 5mL vials of blood which will be separated and the serum and cell pellet will be stored for future analysis. Five skin biopsies will be taken during the study. At week 0, up to two 3mm tissue biopsies will be taken from lesional skin and one biopsy will be taken from normal appearing skin. The initial biopsy of lesional tissue and control will be

annotated. At week 4, up to two 3mm biopsies will be taken from lesional responsive tissue and lesional refractory tissue. Responsive and non-responsive lesions will be determined by the change in Modified CAILS between week 0 and 4. Responsive will require a 50% reduction in Modified CAILS and non-responsive can have progression, no change, or up to a 50% reduction in Modified CAILS. The lesions will be chosen using full body photographs taken at week 0. Up to 60 samples will be snap frozen and stored in the tissue biobank. Once completed, RNA sequencing will be performed on the 60 tissue samples and analysis will be performed. Paired analysis of treatment responsive and refractory lesions will be made as well as treated and untreated lesions.

Nucleic Acid Extractions: RNA will be extracted from a total of 50 um of fresh tissue using the Qiagen FFPE RNeasy Micro extraction Kit according to manufacturer's recommendation.

RNA Transcriptome Sequencing: RNA transcriptome sequencing will be carried out using commercially available techniques. Briefly, RNA Libraries will be created using up to 100ng of RNA as starting material using the Agilent RNA Access Library kit according to manufacturer's recommendation. Libraries will be QCed for quality and quantity using the Agilent BioAnalyzer High Sensitivity Chip. Pair-End sequencing will then be carried out on the Illumina HiSeq 4000 using 101bp insert fragments.

Primary and Secondary Measures:

All efficacy assessments will be performed prior to the administration of study treatment at each visit. The recommended order and the overall outline of measurements for the efficacy assessments are described below.

Efficacy measures: PGA, BSA, Modified CAILS, Pruritus NRS, Skindex-16

To determine the efficacy of INCB018424 PHOSPHATE CREAM as measured by the change in Modified CAILS score of the index treatment and control lesion (weeks 0 and 4) and changes in lesion count (week 0 and 4)

Secondary Outcome Measures: To determine the efficacy of INCB018424 PHOSPHATE CREAM and the duration of response after discontinuation as measured by the change in Pruritus NRS, (week 0 to week 4, week 0 to week 8, weeks 4 to 8, weeks 8 to 12), Change in Skindex-16 (week 0 to week 4, weeks 4 to 8, weeks 8 to 12), Change in Physician Global Assessment (PGA) (week 0 to week 4, week 0 to week 8, weeks 4 to 8, weeks 8 to 12), Change in BSA (week 0 to week 4, week 0 to week 8, weeks 4 to 8, weeks 8 to 12), Change in Modified CAILS (week 0 to week 8, weeks 4 to 8, weeks 8 to 12).

Exploratory Outcome Measures: To predict responses and examine the pharmacodynamics of treatment through the identification of unique biomarkers and transcriptomic changes of LP at week 0 and utilizing RNA sequencing on responsive and non-responsive tissue at week 4 to correlate these biomarkers with measures of global response: Modified CAILS, PGA, BSA, and lesion count.

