4.3 Duration of Participation

The study consists of 3 epochs: screening/washout period (of at least 1 week and up to 4 weeks), treatment epoch (of 8 weeks from screen/washout), and follow up epoch (of 4 weeks). The screening and washout period will allow for treatment naïve/ new diagnosis LP to undergo evaluation and diagnosis and for treatment refractory to undergo a washout. The total duration of the study will be 13-16 weeks.

Tables:

• **Table-1: Prohibited treatment**

Prohibited treatments^{†, ‡}	Washout period (before Randomization Visit)
Any concomitant oral or topical JAK inhibitor	Prohibited
Any biologic drug	Stable dose for 3 months
Immunomodulation treatments for LP [§] [e.g., methotrexate, cyclosporine A, corticosteroids (oral, i.v., intramuscular, s.c., intra-articular, transdermal), mycophenolate mofetil, azathioprine]	4 weeks
Topical treatment that is likely to impact signs and symptoms of LP (e.g., pimecrolimus, tacrolimus)	2 weeks
Non-immunosuppressive agents (tetracycline antibiotics & niacinamide)	2 weeks
Prohibited regimen of Topical Corticosteroids (TCS)	
TCS on any location on body (including face, scalp and/or genitoanal area)	2 weeks

[†] If the prohibited treatment is being used during the study for any indication, the subject must discontinue use of the prohibited treatment if he/she wishes to continue in the study.

[‡] In case of undue safety risk for the subject, the subject should discontinue study treatment at the discretion of the investigator/qualified site staff. If the subject received a live virus vaccination during the study, the subject must discontinue study treatment.

[§]Inhalative CS with only a topical effect (e.g., to treat asthma) are not considered “systemic immunomodulation treatments” and are therefore acceptable as co-medication. Immunosuppressive medication for conditions other than LP will be allowed.

Table-2: Screening and Visits (+/- 2 day window)

	Screening	Day 0	Week 1	Week 2	Week 3	Week 4	Week 8	Week 12

INCB18424		X	X	X	X	X		
Physical Exam	X	X	X	X	X	X	X	X
Adverse Event Assessment		X	X	X	X	X	X	X
Chest X-ray	X							
Assessments: PGA, BSA, lesional number, Modified CAILS, Skindex-16, Pruritus NRS		X	X	X	X	X	X	X
Photographer		X	X	X	X	X	X	X
Skin Biopsy (tissue/serum bank)		X				X		
Urine Pregnancy Test	X							
Venipuncture	X	X	X	X	X	X	X	X
Biomarker/RNAseq blood (tissue/serum bank)		X		X		X		
CMP	X		X	X	X	X	X	X
CBC	X		X	X	X	X	X	X
Quantiferon Gold	X							
Hepatitis B	X							
Hepatitis C	X							

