during or between visits or through physical examination, laboratory test, or other assessments. Please see [Supplemental 3](#) for a detailed description of safety monitoring. Clinically significant abnormal laboratory values or test results will be identified through a review of values outside of normal ranges/clinically notable ranges, significant changes from baseline or the previous visit, or values which are non-typical in patient with underlying disease. Investigators have the responsibility for managing the safety of individual patient and identifying adverse events. Alert ranges for labs and other test abnormalities are included determined by the Mayo Clinic Arizona and Mayo Medical Laboratory. Adverse events will be recorded in the Adverse Events Case Report Form (CRF) under the signs, symptoms or diagnosis associated with them, and severity. All adverse events will be treated appropriately. Once an adverse event is detected, it should be followed until its resolution or until it is judged to be permanent, and assessment should be made at each visit (or more frequently, if necessary) of any changes in severity, the suspected relationship to the study drug, the interventions required to treat it, and the outcome (see [Supplemental 3](#)). Information about common side effects already known about the investigational drug can be found in the package insert. This information will be included in the patient informed consent and should be discussed with the patient during the study as needed. The investigator will also instruct each patient to report any new adverse event (beyond the protocol observation period) that the patient, or the patient's personal physician, believes might reasonably be related to study treatment. This information should be recorded in the investigator's source documents, however, if the AE meets the criteria of an SAE. To ensure patient safety, every SAE (see [Supplemental 3](#) for definition), regardless of suspected causality, occurring after the patient has provided informed consent and after the patient begins taking study drug and until 30 days after the patient has stopped study participation will be recorded and reported to Incyte. Any SAEs experienced after this 30-day period should only be reported to Incyte if the investigator suspects a causal relationship to the study drug. All malignant neoplasms will be assessed as serious under "medically significant" if other seriousness criteria are not met. Medical and scientific judgment will be exercised in deciding whether other situations should be considered serious reactions, such as important medical events that might not be immediately life threatening or result in death or hospitalization but might jeopardize the patient or might require intervention to prevent one of the outcomes listed in SAE. Any suspected transmission via a medicinal product of an infectious agent is also considered a serious adverse reaction. All AEs (serious and non-serious) are captured and recorded, SAEs also require individual reporting (see [Supplemental 3](#)). To ensure patient safety, each pregnancy occurring while the patient is on study treatment must be reported to the sponsor-investigator within 24 hours of learning of its occurrence. The pregnancy should be followed up to determine outcome, including spontaneous or voluntary termination, details of the birth, and the presence or absence of any birth defects, congenital abnormalities, or maternal and/or newborn complications. Pregnancy follow-up should be recorded on the same form and should include an assessment of the possible relationship to the study treatment. Any SAE experienced during the pregnancy and unrelated to the pregnancy must be reported on a SAE form.

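### CBC and CMP are not scheduled at Day 0, so the only pre-dose value is 1 to 4 weeks old and, in some subjects, may reflect a systemic drug being washed out

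*Combined protocol and SAP*

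**What the plan says.** Section 4.1 gives the on-study laboratory schedule: "Laboratory and safety monitoring will occur at weeks 1, 2, 3, 4, and 8, and 12". Week 0 is not in the list. Table-2 (section 4.3) agrees. CBC and CMP are marked at Screening and at weeks 1, 2, 3, 4, 8 and 12, with nothing at Day 0. Day 0 does have a venipuncture, but the only blood test marked for that day is the biomarker/RNAseq bank sample. Section 7.2 says only that blood is drawn at that visit.

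Section 4.3 gives a combined screening and washout epoch, described as a "screening/washout period (of at least 1 week and up to 4 weeks" maximum, and says that it exists in part "for treatment refractory to undergo a washout". Section 4.1 adds that "a washout period of 2 weeks for topical and 4 weeks for systemic agents is required". Table-1 gives examples of the systemic agents with the 4-week washout: "e.g., methotrexate, cyclosporine A, corticosteroids (oral, i.v., intramuscular, s.c., intra-articular, transdermal), mycophenolate mofetil, azathioprine".

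On use of the results, section 2.6 promises that "subjects will be monitored for any signs of inhibition of their blood counts". Section 9.5 lists "significant changes from baseline or the previous visit" as one way of identifying a clinically significant laboratory value. Its other triggers are values outside normal or notable ranges and values atypical for the underlying disease. No section defines the laboratory baseline.

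**The concern.** A change from baseline is informative about the cream only if the baseline shows the subject's state just before the cream. Here the single pre-dose panel can be up to 4 weeks old. If a subject was taking methotrexate, azathioprine or a systemic corticosteroid when it was drawn, counts or chemistry may shift between that draw and Day 0 because the earlier drug was stopped. Recovery from the earlier drug could then hide a fall on the cream. A shift caused by stopping the earlier drug could equally be attributed to the cream.

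Such subjects are foreseeable. Section 2.1 says that refractory disease often needs systemic treatment, including methotrexate, and section 4.1 says that non-responders to standard care will be washed out and enrolled. Section 2.6 lists decreased blood cell count and raised liver enzymes among reported events. The study is single-arm with no vehicle group, so each subject's own values carry the interpretation.

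**Working it through.** **1. Check the epochs against the stated duration.** Section 4.3 gives screening/washout of 1 to 4 weeks, treatment of 8 weeks and follow-up of 4 weeks. The sums are 1 + 8 + 4 = 13 and 4 + 8 + 4 = 16. This reproduces the plan's own figure: "The total duration of the study will be 13-16 weeks". The 1-to-4-week range is therefore the interval from screening to Day 0.

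**2. Count the pre-dose panels.** From Table-2:

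| | Screening | Day 0 | Wk 1 | Wk 2 | Wk 3 | Wk 4 | Wk 8 | Wk 12 |
|---|---|---|---|---|---|---|---|---|
| Venipuncture | X | X | X | X | X | X | X | X |
| CBC, CMP | X | – | X | X | X | X | X | X |

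Screening and Day 0 are the only pre-treatment visits, so there is one pre-dose CBC and one pre-dose CMP, both at Screening.

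**3. Age of that value.** I assume the draw is made at the screening visit that opens the epoch.
- Screening to first dose: 1 × 7 = 7 days to 4 × 7 = 28 days (about 5 to 30 if the ±2-day visit window applies).
- Screening to the first on-treatment panel at week 1: 7 + 7 = 14 to 28 + 7 = 35 days.
- With a Day 0 panel these become 0 days and 7 days.

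**4. Who could have a baseline affected by an earlier drug.** Table-1 counts washout back from a randomization visit, which I take to be Day 0. With an epoch of s weeks and a 4-week systemic washout, the minimum drug-free time at the screening draw is 4 − s weeks:
- s = 1: at least 3 weeks off drug
- s = 2: at least 2 weeks
- s = 3: at least 1 week
- s = 4: possibly 0 weeks, that is, still on drug

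The worst case is a subject still on a systemic agent at screening. That subject needs the whole 4-week epoch, so the draw falls about 28 days before dosing. Section 5.1 requires consent before any study-related activity, so a washout undertaken for the study cannot start before consent.

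**5. Comparators at week 1.** Section 9.5 offers baseline or the previous visit. Day 0 has no panel, so both resolve to the screening sample. From week 2 the previous-visit comparator is an on-treatment value. A baseline comparator remains the screening sample throughout.

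**6. Illustration only; every input is assumed.** Let the post-washout count be 100 and the on-cream count 80, a true change of 80/100 − 1 = −20%.
- Earlier drug lowers the screening count 20%, to 80: apparent change 80/80 − 1 = 0%.
- Earlier drug lowers it 10%, to 90: apparent change 80/90 − 1 = −11%.
- No effect of the earlier drug: apparent change −20%.

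The exact cancellation in the first case follows from choosing two equal percentages. The documents give no size for either effect.

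**The case against.** Much of the case on the other side stands, and it limits the point.

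- A reader might infer that every refractory subject's screening panel is drawn on another drug. The documents do not support that. Section 5.1 defines refractory as failure of at least one established treatment, which may be topical or in the past, and treatment-naïve subjects are also enrolled. No passage says that the screening draw precedes washout. That order is inferred from a single screening visit and a washout placed inside the epoch.
- A reader might infer that section 9.5 judges laboratory values only by change. It does not. Values outside normal or notable ranges are flagged whatever the screening value was.
- A reader might infer that no other off-drug value exists. Treatment ends at week 8, and CBC and CMP are repeated at week 12, 12 − 8 = 4 weeks later. Recovery at that point would help to reveal a drug-related fall, although too late to help interpret the week 1 result.
- Section 2.4 attaches the hematopoietic risk to oral dosing and puts topical exposure several-fold below the level linked to hematologic changes.
- Section 8.2 plans no laboratory change-from-baseline analysis, so no specified analysis is shown to be biased.

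One further defence is weaker. Section 7.2 describes the Day 0 draw in the same words as visits that do include the panels, and section 4.6 and Supplemental 3 speak of hematology and chemistry at all scheduled visits. Those two places defer to Table-2, however, and Table-2 and section 4.1 both omit Day 0.

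**Conclusion.** The point holds in a limited form. As written, the plan has one pre-dose CBC and CMP, 7 to 28 days before the first application, and none after washout. For a subject on, or recently off, a systemic lichen planus agent at screening, that value can reflect the earlier drug. The number of such subjects among the 12 is not given and may be none; each one would be 1/12 = 8.3% of the study. For everyone else the defect is only that the reference is 1 to 4 weeks old.

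What is weakened is the reading of within-subject change, most clearly at week 1, and the attribution that depends on it. The tempting stronger conclusion, that the laboratory safety findings as a whole would be unreliable, does not follow, because range-based flags, later visits and week 12 all remain. The conclusion rests on reading Table-2 and section 4.1 literally, on the screening draw opening the epoch, and on the randomization visit in Table-1 meaning Day 0. Because the remedy costs so little, the change is worth making.

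**What to change.** Mark CBC and CMP at Day 0 in Table-2, on the venipuncture already scheduled. Draw them before the first application, as section 4.6 already requires of all blood draws. Add week 0 to the laboratory list in section 4.1 and name the two panels in section 7.2. State that the Day 0 sample is the laboratory baseline for section 9.5 and for any descriptive laboratory summaries, and keep the screening sample for eligibility.

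The cost is two routine panels per subject, 2 × 12 = 24 in all, with a little more blood from an existing draw and no extra visit or needle stick. Section 4.1 has the Day 0 research blood separated and stored, so a CBC omitted on the day could not be counted on later.
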